Trial Title

Randomized double-blind controlled multicenter trial comparing suture and mesh repair in small umbilical hernias in adults

Trial Code

SUMMER trial

Trial Registration Number

ClinicalTrials.gov Identifier: NCT04231071

SUMMER Trial - Statistical Analysis Plan (SAP)

Randomization

Patient will be allocated through the ECRF-system using pre-generated randomization lists. The randomization will be conducted using a block randomization with 1:1 relationship to the two procedures stratified by centre and defect size (≤ 10 mm and >10 mm). Total concealment of the allocation will be achieved with 4 or 6 block random sequence generation. Blinding of participants and follow-up surgeons with blinding of outcome assessment.

Analysis

• ITT – Intention to treat

All analysis will be made using an intention to treat procedure. Corresponding per-protocol analysis will be made and results from this analysis will be attached as a supplement in the final publication. All statistical tests will be two-sided using a significance level of α = 0.05.

Primary endpoint

To evaluate whether an onlay mesh in the repair of primary small umbilical hernias ≤ 2 cm reduces the risk of recurrence compared to suture repair 1 year and 3 year after surgery.

The primary endpoint is the recurrence rate during a follow-up period of 30 days, 12 and 36 months and will be analyzed using a logistic regression model with dummy variables specifying each time of follow-up. The analysis will be adjusted for centre, defect size and BMI. Reciprocal Kaplan-Meier curves will be generated to illustrate time to recurrence.

In order to detect a difference in recurrence rate of 9 pp after 36 months, assuming a recurrence rate of 3% with the use of mesh and 12% with a suture repair a sample size of 288 (144 in each

Version 1.0 – 2020-01-31

group) will be required to achieve a power of 80% at a significance level of α = 0.05, allowing for a dropout frequency of 10%.

• Secondary endpoints

Secondary outcomes that will be analyzed by comparing the treatment groups are postoperative complications 30 days after surgery (Clavien Dindo scale), postoperative pain 1 year after surgery (assessed with Ventral Hernia Pain Questionnaire), postoperative complications 1 year after surgery. Postoperative complications and postoperative pain will be analyzed using ordinal logistic regression. Presence of postoperative complications will be analyzed using binary logistic regression.

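### The primary endpoint section names no decisive treatment contrast and no row structure, so N = 288 and the 5% error rate hold under some readings of the primary model but not others

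*SAP*

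**What the plan says.** All of this is in the Analysis part of the SAP.

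- **Objective** (Primary endpoint): whether onlay mesh "reduces the risk of recurrence compared to suture repair 1 year and 3 year after surgery".
- **Endpoint** (Primary endpoint): "The primary endpoint is the recurrence rate during a follow-up period of 30 days, 12 and 36 months".
- **Model** (Primary endpoint): a "logistic regression model with dummy variables specifying each time of follow-up", adjusted for centre, defect size and BMI.
- **Display** (Primary endpoint): "Reciprocal Kaplan-Meier curves will be generated to illustrate time to recurrence".
- **Sample size** (Primary endpoint): "In order to detect a difference in recurrence rate of 9 pp after 36 months", with 3% recurrence under mesh and 12% under suture. The total of 288 (144 per arm) includes 10% dropout and "will be required to achieve a power of 80% at a significance level of α = 0.05".
- **Error rule** (ITT paragraph): "All statistical tests will be two-sided using a significance level of α = 0.05".

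The SAP mentions no treatment-by-time term, no within-patient variance, no multiplicity rule and no single deciding test.

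**The concern.** The section uses three sets of time points: 1 and 3 years, then 30 days, 12 and 36 months, then 36 months alone. Visit dummies without a treatment-by-time term point towards one treatment coefficient shared by all visits, but what that coefficient means depends on the rows, which are not defined.

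- **First recurrence per interval.** A patient contributes rows only until recurrence. This is a discrete-time survival model and fits the time-to-recurrence display.
- **Cumulative status at each visit.** A patient who recurs by 12 months counts as an event at 12 and again at 36 months. The rows are then correlated, and the SAP states no variance that allows for this.
- **Separate tests by visit.** This is less well supported. It rests on the two time points in the objective and on the blanket 0.05 rule.

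An analyst could choose among these after seeing the data. At stake is the error rate of the trial's decisive test.

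**Working it through.** **Inputs.** From the SAP: 3% vs 12% at 36 months, two-sided 0.05, 80% power, 144 per arm, 10% dropout. This leaves 144 × 0.9 = 129.6, taken as 130 assessed per arm. Recurrence rates before 36 months are not in the SAP; all those below are assumptions, written as 30 days/12 months/36 months in %.

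**1. The SAP's own figure.** Unpooled normal approximation: n = (1.960 + 0.842)² × (0.03 × 0.97 + 0.12 × 0.88) / 0.09² = 7.849 × 0.1347 / 0.0081 = 130.5, so 131 per arm. Then 131 × 1.1 = 144.1, which matches 144; dividing by 0.9 gives 146 per arm, 292 in total. At 129.6 per arm the pooled-variance formula gives power 78.9%. The 288 is reproduced, for 36 months only.

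**2. 36 months alone.** Exact enumeration at 130 per arm gives power of 78.4% (Wald), 81.7% (Pearson) and 83.3% (likelihood ratio, LR). Size at a common 12% is 4.5%, 4.9% and 5.1%. The plan holds.

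**3. Discrete-time first recurrence, one coefficient.** In 40,000 unadjusted runs per scenario, type I error is 4.1–5.4% and power 75–78% (Wald) or 82–84% (LR). The median odds ratio is 4.33–4.52, against (0.12/0.88)/(0.03/0.97) = 4.41 at 36 months. Adjusted for centre (6 or 12 assumed), defect size and BMI, Wald type I error is 5.6–5.8%. The plan roughly holds.

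**4. Stacked cumulative rows treated as independent.** Let p₁, p₂, p₃ be the cumulative rates under the null. The naive variance per patient is V = Σpₜ(1 − pₜ). The true variance adds 2C, where C = Σ pₛ(1 − pₜ) over s < t, because recurrence by an earlier visit implies recurrence by a later one. With R = (V + 2C)/V, the actual type I error is about 2[1 − Φ(1.96/√R)].

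| Null rates | V | C | R | Approximate error | Simulated |
|---|---|---|---|---|---|
| 1/6/12 | 0.1719 | 0.0710 | 1.83 | 14.7% | 14.1% |
| 2/8/12 | 0.1988 | 0.1064 | 2.07 | 17.3% | 17.2% |
| 1/4/12 | 0.1539 | 0.0536 | 1.70 | 13.2% | 12.8% |
| 1/4/7.5 | 0.1177 | 0.0559 | 1.95 | 16.0% | 15.2% |

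With covariate adjustment the simulated error is 15.3–17.8%. It is inflated under every null timing tried.

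**5. The same rows with patient-clustered variance.** Unadjusted type I error is 4.7–5.4% (5.8–7.0% with covariates, Wald). Power depends on when recurrences occur:

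| Assumed effect | Suture vs mesh | Power |
|---|---|---|
| Proportional | 1/6/12 vs 0.25/1.5/3 and two similar | 68–71% Wald, 75–77% score |
| Late | 1/4/12 vs 1/2/3 and two similar | 39–49% Wald, 52–61% score |
| Early | 12 months: 8–10 vs 1 or less; 36 months: 12 vs 3 | about 83–93% |

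One more extreme late pattern (0.6/3/12 vs 0.6/2.7/3) gave about 33%.

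**6. Success at either 12 or 36 months, 0.05 each.** Family-wise error under the same four nulls is 5.9–7.3% (Wald), 7.8–8.5% (Pearson) and 8.3–10.4% (LR). If the tests were independent it would be 1 − 0.95² = 9.75%. The LR figures include that test's own size at 12 months, 5.5–6.6%.

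**The case against.** The strongest reply is that the time points can coexist. The objective's 1 and 3 years are two of the three visits, the sample size uses the end of follow-up, and a single discrete-time coefficient would serve all of them. On that reading N and alpha roughly hold. This stands: a reader might infer three rival endpoints, and the text does not compel that. What remains is that the SAP never says this is the model meant, and the same sentence also fits stacked cumulative rows in ordinary logistic software.

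A reader might also infer that the trial is underpowered. The SAP does not support that. The 288 is right for its stated inputs. Clustered stacked power ranges from poor to better than planned according to timing that the SAP does not give, so no flat statement about it is possible.

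The visit-wise readings are the least supported, and by Wald their inflation is small (at most 7.3%). They show that the blanket 0.05 rule leaves the 12-month claim unprotected; they do not show that such a claim is planned.

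Finally, the protocol was not available and may name the time point. That could settle the intent, but the SAP itself sets out the endpoint, model, alpha and sample size, and should fix how they fit together.

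**Conclusion.** The concern holds in a limited form. The primary analysis lacks a named deciding contrast, a row definition and a rule for repeated rows. The planned size and error rate are sound for 36 months alone and roughly sound for a discrete-time first-recurrence model.

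The firmest adverse result is the 13–18% type I error of stacked rows treated as independent. It follows from the overlap of cumulative events and appeared under every null timing tried. The 6–10% family-wise error for either-visit success depends on the test chosen. Both use assumed early rates and 130 assessed per arm. Because a literal fit of the stated model can more than double the nominal error of the decisive test, this should be settled before the data are analysed.

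**What to change.** Change the SAP wording and leave N at 288. Suggested text:

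> The single primary test, at two-sided 0.05, is the treatment effect on recurrence by 36 months, from a logistic regression adjusted for centre, defect size and BMI. Recurrence at 12 months is tested at 0.05 only if the 36-month test is significant. Recurrence at 30 days is described only.

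Align the objective sentence with this, name the test (Wald or LR), and state how patients lost before 36 months are handled.

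If the time-dummy model is to stay primary, state instead that it is a discrete-time model with rows only until first recurrence and that its one treatment coefficient is the only primary test. Do not fit a 30-day treatment-by-time term. At 1% vs 0.25%, the chance that at least one arm has no 30-day event is 1 − (1 − 0.99¹³⁰)(1 − 0.9975¹³⁰) = 80%; at 2% vs 0.5% it is 56%.

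**Cost.** The sponsor gives up a free-standing confirmatory claim at 12 months. With 6 or 12 centres assumed, the adjusted 36-month test has power of about 77% (Wald, type I error 4.5–5.6%) or 82% (LR, 5.2–6.4%). Some centre has no recurrence in 21% of runs with 6 centres and 92% with 12; this sparsity exists under the present text too.

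**Limit of the gate.** It protects the 36- and 12-month hypotheses only as well as each test holds its own size. With a true 36-month effect and 2% recurrence in both arms at 12 months, the false 12-month claim rate by LR is 6.6%.

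### The trial is sized on a 9 pp difference, but the SAP plans no estimate on that scale and no provision for an arm without recurrences; both are cheap to add

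*SAP*

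**What the plan says.** All of this is in the SAP, Analysis, Primary endpoint.

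- **Objective:** whether mesh "reduces the risk of recurrence compared to suture repair 1 year and 3 year after surgery".
- **Endpoint:** "The primary endpoint is the recurrence rate during a follow-up period of 30 days, 12 and 36 months".
- **Model:** the endpoint "will be analyzed using a logistic regression model with dummy variables specifying each time of follow-up". Three adjustment terms are named: BMI, centre and defect size.
- **Sizing:** the target is worded as "In order to detect a difference in recurrence rate of 9 pp after 36 months". The rates behind that target are given as "assuming a recurrence rate of 3% with the use of mesh and 12% with a suture repair". The total is 288, or 144 per arm, with power 80%, alpha 0.05 and dropout 10%.

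The only other output for this endpoint is a set of Kaplan-Meier curves, described as illustration. The section names no test type (Wald or likelihood ratio), no interval method, no rule for sparse events and no risk difference.

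**The concern.** There are two gaps.

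**Scale.** The design question is an absolute difference of 9 pp at 36 months, and the planned model returns an odds ratio. This applies in every trial, whatever the data turn out to be.

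**Sparse events.** With about four recurrences expected on mesh, having none is a realistic outcome. Maximum likelihood then puts the odds ratio at 0, with no finite log odds ratio and no Wald interval. If nothing is fixed beforehand, the fallback for the primary analysis is chosen after the data have been seen. Even without an empty arm, the choice of test is open, and the candidate tests differ in power on the same data.

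**Working it through.** **Inputs (all from the SAP).** 144 per arm, 10% dropout, 3% and 12% at 36 months, two-sided alpha 0.05, 80% power.

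**The SAP's sample size.** With unpooled variance, n = (1.96 + 0.842)^2 x (0.12 x 0.88 + 0.03 x 0.97) / 0.09^2 = 7.85 x 0.1347 / 0.0081 = 130.5, so 131 per arm. Dividing by 0.9 gives 146 per arm, 292 in total, within 2% of the stated 288. (130.5 x 1.1 = 143.6 gives 144 exactly.) The sizing is therefore a comparison of two proportions on the difference scale.

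**Expected events.** 144 x 0.9 = 129.6, about 130 evaluable per arm. Mesh: 130 x 0.03 = 3.9. Suture: 130 x 0.12 = 15.6. Total: 19.5.

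**Chance of no mesh recurrence.** 0.97^130 = 1.9%; with all 144 followed, 0.97^144 = 1.2%.

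**Comparison of methods.** Every pair of binomial counts at 130 per arm was enumerated, without covariates. In this two-arm case Firth's estimate equals adding 0.5 to each cell. The true log odds ratio is ln[(0.03/0.97)/(0.12/0.88)] = -1.484, an odds ratio of 0.227. Null rejection takes 7.5% in both arms.

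| Test | Power | Null rejection |
|---|---|---|
| Wald (no finite estimate = not significant) | 78.4% | 4.3% |
| Penalised likelihood ratio (Firth) | 81.2% | 4.6% |
| Ordinary likelihood ratio | 83.3% | 5.5% |
| Risk difference, HC3 | 81.7% | 4.9% |

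**Bias.** In the same finite trials the mean log odds ratio is -1.563 with maximum likelihood (5.4% too far from no effect) and -1.445 with Firth (2.6% too close). The mean odds ratio is 0.250 with maximum likelihood (finite trials) and 0.267 with Firth (all trials), so Firth is further from 0.227.

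**Example, 0/130 mesh against 15/130 suture.** The ordinary odds ratio is 0, with only an upper profile limit, 0.12. Firth gives 0.029 (0.0002 to 0.22). The risk difference is -11.5 pp. Its HC3 standard error is sqrt(0.1154 x 0.8846 / 130) / (1 - 1/130) = 2.82 pp, so the interval is -17.1 to -6.0. The empty mesh arm adds nothing to that standard error.

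**Intervals when mesh has no recurrence.** Overall, the HC3 interval covers the true -9 pp in 94.7% of trials. Among trials with no mesh recurrence it covers when suture has 7 to 19 recurrences: 85.3% - 0.3% = 85.0% under Binomial(130, 0.12).

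The Miettinen-Nurminen score interval is a natural substitute but does not help here. At a difference of -9 pp its constrained mesh risk is also 0 (for up to 22 suture recurrences). Its standard error is then sqrt(0.09 x 0.91 / 130 x 260/259) = 2.51 pp. It covers when the suture proportion lies within 9 +/- 4.93%, which is 6 to 18 recurrences, or 78.6%.

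The Agresti-Caffo interval adds one recurrence and one non-recurrence to each arm, so the empty arm has a variance. In the example: 1/132 - 16/132 = -11.4 pp, standard error sqrt(0.0076 x 0.9924 / 132 + 0.1212 x 0.8788 / 132) = 2.94 pp, interval -17.1 to -5.6. It covers for 7 to 20 suture recurrences: 90.4% - 0.3% = 90.0%. No method guarantees 95% after selecting on an extreme result.

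**The case against.** The strongest reply is that nothing here is wrong. An adjusted logistic regression suits a binary endpoint, and a power calculation in percentage points does not oblige anyone to estimate a risk difference. The Kaplan-Meier curves will show absolute recurrence by arm. If mesh has no recurrence, an ordinary likelihood-ratio test still rejects in more than 99.99% of such trials and the profile interval still gives an upper limit. The SAP names no test, so the Wald failure is conditional. All of this stands, and it limits the point to an improvement. It does not supply an interval on the 9 pp scale: the curves are illustrative and no contrast is planned from them.

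A reader might infer more than the SAP supports:

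- **That the planned test is invalid.** It is not. About 98% of trials give a finite estimate, and the null rejection rates above are 4.3% to 5.5%.
- **That Firth is justified by lower bias.** The advantage depends on the scale and on which trials are counted, and it reverses for the mean odds ratio.
- **That trials without a mesh recurrence carry the strongest evidence for mesh.** Not so: 2/130 against 24/130 has a larger likelihood-ratio statistic (24.0) than 0/130 against 15/130 (21.7).
- **That the problem is much larger at 1 year.** If the 1-year mesh rate were 1% to 2%, no mesh recurrence would occur in 0.99^130 = 27% to 0.98^130 = 7% of trials. Those rates are assumed. The SAP mentions visit dummies, not a separate treatment effect per visit. With one common effect, only the 2% applies.

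**Conclusion.** The point holds as a low-cost improvement. The missing estimate on the design scale affects every trial. The sparse-event gap affects about 1.9% of trials at 130 per arm, or 1.2% with complete follow-up. The case for Firth is a finite estimate, 2.8 points more power than Wald (81.2% against 78.4%) and null rejection of 4.6% against 5.5% for the ordinary likelihood ratio.

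These figures assume that the SAP's 3% and 12% are true and leave out covariates. Simulations with visit dummies and 2 to 12 centres kept the same order of power: Wald 72.9-79.8%, penalised 78.9-82.2%, ordinary likelihood ratio 80.9-85.6%. No finite maximum-likelihood estimate arose in 2.0-3.7%. The number of centres, the spread between them, the covariate effects and the timing of recurrences were assumed there, so these ranges are only supportive.

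**What to change.** Add to the SAP, Primary endpoint:

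1. **Risk difference.** Report the adjusted 36-month risk difference with a 95% interval, from a linear model with the same covariates and HC3 standard errors. If an arm has no recurrence, give instead an interval that allows for that arm's uncertainty. Agresti-Caffo is one choice; it is unadjusted, and the SAP should say so. Do not derive the difference from raw Firth predictions, which overstate risk: (3.9 + 0.5)/131 = 3.36% and (15.6 + 0.5)/131 = 12.29% average 7.8%, against 7.5%.
2. **Logistic model.** Keep the covariates, fit with Firth penalisation, and use the penalised likelihood-ratio test and profile interval.
3. **Repeat records.** If the visit dummies are kept, either end each patient's records at first recurrence or use a method that allows for the correlation. Ending records makes the effect a discrete-time hazard odds ratio rather than an odds ratio for 36-month recurrence, and the SAP should state this.

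The cost is a few sentences and standard software. Data, visits, covariates and sample size do not change. The downsides are slight shrinkage, a mean odds ratio somewhat closer to 1, and about 2 points less power than an ordinary likelihood-ratio test.

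### Do the planned recurrence curves need a written rule for event dates, censoring dates and cut-off?

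*SAP*

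**What the plan says.** Under Analysis, Primary endpoint, the SAP defines the outcome by follow-up time: "The primary endpoint is the recurrence rate during a follow-up period of 30 days, 12 and 36 months". The analysis is "a logistic regression model with dummy variables specifying each time of follow-up", adjusted for centre, defect size and BMI. One further sentence introduces the figure: "Reciprocal Kaplan-Meier curves will be generated to illustrate time to recurrence". Nothing else in the SAP concerns the curves.

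The sample size paragraph supplies the expected levels, "assuming a recurrence rate of 3% with the use of mesh and 12% with a suture repair", for a difference at 36 months. It asks for 144 patients per group and allows for 10% dropout.

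**The concern.** A Kaplan-Meier estimate is defined by its event and censoring times. A recurrence first seen at the 36-month visit may have arisen at any time since the 12-month visit, so the data behind the curve are interval-censored, and the SAP does not say how to date them.

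One possible choice does harm. If each patient is dated at the actual 36-month visit, those seen early without recurrence leave the risk set, and recurrences found later are divided by the few who remain. The curve is then too low at exactly 36 months, because about half the visits are still to come, and too high afterwards. The only figure planned for the primary endpoint could then disagree visibly with the 36-month proportions from the primary analysis. The choice could also be made after the data are seen.

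**Working it through.** **Inputs from the SAP:** 144 per arm; 36-month risks of 12% (suture) and 3% (mesh); 10% dropout; assessments at 30 days, 12 and 36 months.

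**Assumptions not in the SAP:** actual visit dates spread evenly around 36 months; all recurrences found at visits; a share *s* of 25, 50 or 75% of recurrences arising after 12 months.

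**1. The plan's own figure.** Two proportions, two-sided 5%, 80% power, unpooled variance:

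n = (1.960 + 0.842)² × (0.03 × 0.97 + 0.12 × 0.88) / 0.09² = 7.849 × 0.1347 / 0.0081 = 130.5, so 131 per arm.

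131 × 1.1 = 144.1, which matches 144 per arm and 288 in total. The curves play no part in this calculation.

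**2. Scheduled times.** With every event and censoring set to the scheduled visit, simulation gives 12.0% and 3.0% at 36 months. There is no bias.

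**3. Actual dates, by hand, for suture with s = 50%.**
- Recurrence-free after the 12-month visit: 1 − 0.06 = 0.94.
- Risk of a finding at the 36-month visit: q = 0.06 / 0.94 = 0.0638.
- Number at risk entering the 36-month window: about 144 × 0.9 × 0.94 = 122.
- When a fraction f of these is still at risk, the survival curve is about 0.94 × f^q.

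| Place on the curve | f | 1 − 0.94 × f^0.0638 | Simulated |
|---|---|---|---|
| 36.0 months, half the visits done | 0.5 | 10.1% | 10.2% |
| 29 still at risk (20% of 144) | 29/122 | 14.2% | 14.5% |
| 10 still at risk | 10/122 | 19.9% | 20% |

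Only f enters the formula, so the width of the visit window does not matter. Simulated windows of ±1, ±2 and ±3 months give nearly the same levels.

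**4. Simulated range for s = 25 / 50 / 75%.**

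| Place on the curve | Suture (true 12%) | Mesh (true 3%) |
|---|---|---|
| 36.0 months | 11.3 / 10.2 / 9.1% | 2.9 / 2.6 / 2.3% |
| At least 29 at risk | 13.5 / 14.5 / 15.5% | 3.5 / 3.7 / 4.1% |
| At least 10 at risk | 16.5 / 20 / 24% | 4.3 / 5.4 / 6.5% |
| Last patient, mean | 24 / 34 / 42% | 6.3 / 9.6 / 12.4% |
| Last patient, median | 18 / 27 / 35% | 3.8 / 5.2 / 7.0% |

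The means at the last patient are pulled up by the 3 to 9% of suture runs that end at 100% because the final patient at risk has the event.

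**5. Size at the SAP's own horizon.** At 36.0 months the suture curve is 12 − 11.3 = 0.7 to 12 − 9.1 = 2.9 points low. The sampling standard deviation of a 12% risk is √(0.12 × 0.88 / 144) = 2.7 points, or 2.9 points with 144 × 0.9 = 129.6 patients. The error is therefore at most about one standard deviation. The gap between the arms reads 11.3 − 2.9 = 8.4, 10.2 − 2.6 = 7.6 or 9.1 − 2.3 = 6.8 points instead of 9, in the same direction.

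**6. Variations.** If half of the recurrences are found and dated between visits, suture reads 11.7 / 11.2 / 10.7% at 36.0 months, an error of 0.3 to 1.3 points. If visits run one month late on average (s = 50%), it reads 8.0%, which is 4 points low.

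**The case for a change.** The strongest argument for a change is that dating and censoring rules belong in an SAP. This SAP introduces the curve itself, so a visit schedule in the protocol would not settle how the analysis dates events. A suture curve ending at 20 to 40% beside an analysed proportion near 12% would mislead readers, narrow visit windows would not prevent it, and one sentence would.

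Much of this is right. The omission is real, the mechanism is real and the arithmetic reproduces. What does not stand is the step from silence to error. The large figures need three things together: actual visit dates, recurrences found mostly at visits, and a curve drawn to the last few patients after 36 months. The SAP states none of these. It does not say that recurrences are detected only at visits, and one found between visits has a date of its own. A curve stepped at the scheduled times fits the preceding sentence of the SAP, where the model uses "logistic regression model with dummy variables specifying each time of follow-up".

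Nor is the remedy clear-cut if it offers either a life table or an interval-censored (Turnbull) estimate. That leaves open the choice it is meant to close. In an approximate run the Turnbull curve was close at 36.0 months (about 11.9%) but also rose at its end, to 21 to 30% for suture. Scheduled times, or a stop at 36 months, do the real work.

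**Conclusion.** No change to the plan is needed. The SAP leaves a dating, censoring and cut-off convention unwritten for a figure described as illustrative. No test, estimate or decision rests on it. The logistic model, its test and the sample size are unaffected under any choice, and mesh stays below suture on average at every point simulated.

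On the unfavourable reading, the suture curve is about 0.7 to 3 points low at 36.0 months (4 points if visits run a month late). Serious inflation appears only beyond 36 months, where few patients remain at risk. On the natural reading, with scheduled times, the bias is nil. These sizes rest on the assumed spread of visits, detection at visits and timing of recurrences, none of which the SAP gives. An analyst who dates events and censorings at the scheduled visits and ends the curve at 36 months stays within the plan as written.

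### The secondary logistic models name no covariates although randomisation is stratified by centre and defect size, so their tests are somewhat conservative if centres differ in outcome

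*SAP*

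**What the plan says.** Under Randomization, the SAP prescribes "block randomization with 1:1 relationship to the two procedures stratified by centre and defect size", with the defect-size cut at 10 mm and "4 or 6 block random sequence generation".

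Under Primary endpoint, directly after the primary model, it says "The analysis will be adjusted for centre, defect size and BMI". This is the only sentence on covariates.

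Under Secondary endpoints, the outcomes are introduced as a comparison of groups: "Secondary outcomes that will be analyzed by comparing the treatment groups are postoperative complications 30 days after surgery", followed by pain and complications at 1 year. The models are then named: "Postoperative complications and postoperative pain will be analyzed using ordinal logistic regression" and "Presence of postoperative complications will be analyzed using binary logistic regression". No covariates are listed.

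Rules meant for every analysis stand under the general Analysis heading, for example "All statistical tests will be two-sided using a significance level of α = 0.05". Covariate adjustment is not among them.

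**The concern.** Blocking within centre and defect size keeps the two arms balanced inside each stratum. If the strata predict the outcome, this lowers the true variance of the treatment comparison. A logistic model with treatment alone does not see this: its standard error is computed as if patients had been randomised without strata. The standard error is then too large, the test rejects less often than the planned 5% under the null, and power is lost.

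Complications and pain are the endpoints where a disadvantage of mesh would show, and a conservative test makes a real difference easier to miss. A second, smaller consequence is that the primary odds ratio would be conditional on centre, defect size and BMI while the secondary odds ratios would be marginal, so the two would not be on the same scale.

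**Working it through.** **Inputs from the SAP.** 288 patients, 1:1, blocks of 4 or 6 within centre by defect size, two-sided α = 0.05. The 288 itself reproduces closely: (1.960 + 0.842)² × (0.12×0.88 + 0.03×0.97) / 0.09² gives 131 per arm; 131/0.9 gives 146 per arm, 292 in total, 1.4% above the stated figure. The present point does not depend on it.

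**Inputs that are assumed.** The SAP does not give the number of centres, the secondary event rates or the spread between centres. Spread is expressed as the SD of centre effects on the log-odds scale: 0 (none), 0.5 (moderate), 1.0 (strong).

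**Step 1: large-sample formula (binary outcome).** Let r be the between-centre share of outcome variance, r = Var(p_centre) / [p̄(1 − p̄)]. With arms balanced within centre, the true variance is about (1 − r) times the variance the treatment-only model reports, so

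actual size = 2 × [1 − Φ(1.96 / √(1 − r))].

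| Event rate in a typical centre | r at SD 0.5 | size | r at SD 1.0 | size |
|---|---|---|---|---|
| 10% | 0.025 | 4.7% | 0.109 | 3.8% |
| 20% | 0.040 | 4.55% | 0.145 | 3.4% |
| 30% | 0.049 | 4.4% | 0.162 | 3.2% |

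For example, 1.96/√(1 − 0.145) = 1.96/0.925 = 2.12, whose two-sided tail is 3.4%.

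**Step 2: simulation.** 5000 trials per setting; 8 centres with 25, 20, 15, 12, 10, 8, 6 and 4% of patients; defect-size odds ratio 1, 1.5 or 2 alongside SD 0, 0.5 or 1.0; BMI without effect; Wald tests. The treatment odds ratio for power was 2.04 (2.76 at 10% events). The ordinal outcome had upper-tail probabilities of 25, 12 and 5%. Each cell shows treatment-only / adjusted with a random centre intercept, in %.

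| | none | moderate | strong |
|---|---|---|---|
| Type I, binary 25% | 4.8 / 4.8 | 4.4 / 4.8 | 3.8 / 4.9 |
| Type I, binary 10% | 4.2 / 4.4 | 4.1 / 4.4 | 3.2 / 3.9 |
| Type I, ordinal | 4.7 / 4.9 | 4.1 / 4.8 | 3.7 / 4.8 |
| Power, binary 25% | 80.3 / 80.8 | 75.7 / 77.0 | 64.9 / 70.3 |
| Power, binary 10% | 88.4 / 88.3 | 84.2 / 84.9 | 74.8 / 77.5 |
| Power, ordinal | 82.9 / 82.9 | 77.6 / 79.3 | 68.1 / 75.0 |

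The power gain from adjusting is −0.1 to 0.4, 0.6 to 1.6 and 2.8 to 6.9 points (computed before rounding, so up to 0.1 off the table). The Monte Carlo standard error is about 0.3 points at 5% and 0.14–0.45 points for the paired gains. With 4 or 12 centres (binary, 25%) the gains are 1.2–1.4 points moderate and 4.7–5.5 strong.

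**Step 3: defect size alone.** With no centre differences, adjusting by fixed terms gains 1.0 point at a defect-size odds ratio of 1.5 and 1.2 at 2, against 1.0 when defect size has no effect. Defect size therefore adds at most 0.2 points. Centre is what matters.

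**Step 4: separate check of the random-intercept model.** An independent simulation (8 unequal centres, binary, 25%) gave type I error of 5.3 / 5.5, 4.9 / 5.3 and 3.8 / 4.8%, and power of 79.7 / 80.0, 75.7 / 77.5 and 64.9 / 70.5%. This agrees with step 2 within Monte Carlo error.

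**Step 5: where the power comes from.** With strong centre differences and binary 25% events, the median log odds ratio (SE) moves from 0.60 (0.26) to 0.70 (0.28). The ratios are 0.60/0.26 = 2.31 and 0.70/0.28 = 2.50: the standard error rises a little and the estimate rises more.

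**The case against.** The strongest counter-argument is that the SAP never says the secondary models are unadjusted. It is silent, the covariates a few lines earlier may be meant to carry over, and the protocol might say so. The text allows this reading but does not support it: the adjustment sentence refers to one analysis, under one endpoint, while rules for all analyses are placed and worded as such.

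It is also fair that nothing here is an error. A test slightly below 5% does not breach the α rule, the marginal odds ratio is valid, and the SAP claims no power for these endpoints. What remains is a loss of efficiency, and a noticeable one only under strong centre differences, which nothing in the SAP indicates. All of this stands and sets the priority.

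Part of the low type I error at 10% events has another cause. It is already 4.2% with no centre effect, and with moderate differences omission alone predicts about 4.7% (r ≈ 0.5² × 0.10 × 0.90 = 0.0225). The 4.1% seen there is mostly sparse-outcome Wald behaviour and simulation noise. The effect of omission is better read from the change across columns in step 2: 0.1–0.6 points from none to moderate and 1.0 from none to strong.

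On the remedy, BMI is not a stratification factor and had no effect in these runs; it is included only to match the primary model. The SAP does not say how centre enters the primary model, so a random intercept could make the two differ. The independent check of the random intercept covered the binary model at 25% events, not 10% events or the ordinal model.

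**Conclusion.** The point holds as a minor one. As written, the secondary models omit the factors by which patients were randomised, and their tests are conservative if centres differ in outcome: type I error of about 4.1–4.7% with moderate and 3.2–3.8% with strong differences, across the formula and the main simulation. The matching power loss is about 1 and about 3 to 7 points. It is essentially nil if centres do not differ.

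These sizes rest on assumed centre numbers, event rates and centre spread; the direction does not. The validity of the trial and the primary endpoint are not affected.

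**What to change.** Add to Secondary endpoints: *The secondary ordinal and binary logistic models include treatment, defect-size group (≤10 / >10 mm), BMI and centre, the covariates of the primary analysis, with centre as a random intercept. The adjusted odds ratio is the main result; unadjusted group proportions are reported beside it.* State in the same edit how centre enters the primary model, so that any difference is deliberate.

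The random intercept needs no pooling rule and works for binary and ordinal outcomes alike. Fixed centre terms ran at 4.1–5.2% type I error with 8 centres (up to 5.6% with 12). With small centres pooled by size, a centre coefficient still diverged in 0–15% of null trials at 25% events and 20–65% at 10%. If fixed terms are preferred, combine small centres by a rule based on size only, set before unblinding, and use the random intercept where the outcome is sparse.

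The cost is a short text change and no new data. The odds ratio becomes conditional, so part of its larger value reflects a change of estimand, and its standard error rises slightly (0.28 against 0.26 in the strong binary 25% setting).
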